3.2. Exclusion Criteria

Subjects who meet any of the following criteria are not eligible for enrollment as study participants:

- History of severe anaphylaxis to peanut as defined by hypoxia, hypotension, or neurological compromise (Cyanosis or SpO₂ < 92% at any stage, hypotension, confusion, collapse, loss of consciousness; or incontinence)
- Currently participating in a study using an investigational new drug.
- Participation in any interventional study for the treatment of food allergy in the past 12 months or while participating in this study.
- Poor control or persistent activation of atopic dermatitis.
- Diagnosis of persistent asthma as defined by NHLBI criteria and currently being treated with daily doses of inhaled corticosteroids or requiring a rescue inhaler more than 2 days per week.
- Inability to discontinue antihistamines for skin testing and Oral Food Challenges (OFCs).
- Pregnant female.
- Chronic medical condition requiring frequent use of oral steroids, chronic psychiatric illness or history of substance abuse.
- Active eosinophilic esophagitis requiring medication therapy during the past 12 months
- Subjects with known oat or wheat allergy
- Subjects currently on the build-up phase of environmental allergy immunotherapy injections
- Live more than 175 miles away from Texas Children's Hospital located in the Medical Center.

NOTE:

Treatment of glucocorticoids (i.e. prednisone, methylprednisolone, and prednisolone) is permitted while on the study for subjects with wheezing and/or undiagnosed asthma. The dosing allowed will be no more than 2 mg/kg up to 21 days. Subjects will be taken off the study if treatment with any dose of steroid is required for greater than 21 days or if oral systemic corticosteroids are required greater than twice per year for asthma exacerbations.

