- Targeted History and Physical Exam and Diet History: A brief medical and diet history will be obtained and a focused physical exam will be performed.
- Epinephrine injector will be checked for expiration date and parent/guardian will demonstrate proper use.
- Review Home Symptom Diary: At each visit we will review any symptoms experienced while taking the food protein.
- Administer Peanut Equivalent Dose: The first dose of the peanut equivalent will be given in the hospital setting followed by a 2 hour observation period.
- Urine Pregnancy Test: For females of reproductive potential a urine pregnancy test will be performed at month 0 and month 12 visits. If the subject is pregnant she will be dismissed from the study.

6.6. 0 Month Maintenance Study Food Challenge Visit (approximately 9 hours)

- The food challenge will need to be completed within 1 month of the "Month 0" visit.
- Amount of blood to be drawn: At this visit, we will draw up to 4-6 tablespoons of blood (based on the subject's weight) for peanut-specific IgE, IgG, and IgG4 and cellular immune studies, and basophil histamine release assays
- Spirometry or Peak Flow: Spirometry will be attempted in all participants. If valid spirometry results are not successfully obtained, the attempt is documented and peak flow measures will be accepted for the entry criteria with results >90% of predicted. For participants that are able to complete spirometry, FEV1 must be greater than 90% predicted on the day of the challenge to participate in the food challenge.

- Targeted History and Physical Exam and Diet History: A brief medical and diet history will be obtained and a focused physical exam will be performed.
- DBPCFC: The subject will come to Texas Children's Hospital in Houston for a Double Blind Placebo Controlled Food Challenge (DBPCFC) to the study protein (peanut) to determine if he or she is still allergic to peanut or can tolerate peanut.

The DBPCFC visit will last approximately 9 hours. The food challenge may be performed in one day or split into two days. The subject will discontinue antihistamines (for example Zyrtec or Claritin) for 7 days before the procedure and must be off oral corticosteroids for one month before the food challenge.

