No subject initiating therapy in this trial will be replaced. The stopping rules for individual subjects are as follows:

- Greater than or equal to four missed or 'no-show' appointments and four missed home doses,
- Greater than 4 instances of not having or carrying an unexpired epinephrine injector to appointments
- Anaphylactic reaction listed as a Grade 4 as defined by the World Allergy Organization grading scale for systemic reactions to immunotherapy related to peanut OIT dosing at any stage of the protocol.
- Any participant is diagnosed with eosinophilic esophagitis
- Any participant is diagnosed with moderate to severe asthma based on the NHLBI guidelines
- Any participant needs treatment with greater than medium daily doses of inhaled corticosteroids, as defined by the NHLBI guidelines
- Any participant has an accidental peanut ingestion with anaphylaxis during the time on oral desensitization

Participants may be prematurely terminated from the study if:

- The participant elects to withdraw consent from all future study activities, including follow-up
- The participant is “lost to follow-up” (i.e., no further follow-up is possible because attempts to reestablish contact with the participant have failed)
- The participant dies

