6.12. Follow-up of Discontinued Participants

Participants who prematurely discontinue treatment with study drug will remain in the study until normal termination. Subjects may receive the option of receiving a peanut equivalent if indicated. All willing subjects will be followed for the duration of the study, and continue blood draws for mechanistic studies while on a peanut restricted diet, and be monitored for accidental ingestions and safety parameters.

Procedure	Screening (Visit 1)	Entry Oral Food Challenge (Visit 2)	Buildup Phase Visit #3-28 (Weeks 0-50)	0 month of maintenance phase (Visit 29)	0 Month DBPCFC (Visit 30)	6 months maintenance phase (Visit 31)	12 months maintenance phase (Visit 32)	18 months maintenance phase (Visit 33)	24 months maintenance phase (Visit 34)	25 months maintenance phase (Visit 35)	End of Study Visit (Visit 36)	Unscheduled visits
Medical/Allergy Hx	X											
Spirometry or Peak Flow	X	X	X	X	X	X	X	X	X	X	X	X
Physical Exam	X	X	X	X	X	X	X	X	X	X	X	X
Diet Hx	X	X	X	X	X	X	X	X	X			X
Targeted Hx		X	X	X	X	X	X	X	X	X	X	X
Review Home			X	X	X	X	X	X	X			X
FAQLQ/F AIM											X	
Endpoint titration	X		X ¹	X			X		X	X		
Texas Children's Hospital in Houston OIT Administration			X	X ⁷							X	X
OIT Maintenance				X	X	X	X	X				
Entry Oral Food Challenge (1 gram of peanut protein)		X										
Oral food challenge					X				X	X		

Procedure	Screening (Visit 1)	Entry Oral Food Challenge (Visit 2)	Buildup Phase Visit #3-28 (Weeks 0-50)	0 month of maintenance phase (Visit 29)	0 Month DBPC FC (Visit 30)	6 months maintenance phase (Visit 31)	12 months maintenance phase (Visit 32)	18 months maintenance phase (Visit 33)	24 months maintenance phase (Visit 34)	25 months maintenance phase (Visit 35)	End of Study Visit (Visit 36)	Unscheduled Visit
Blood draw for immune cell studies		X	X ³		X	X	X	X	X	X		
Buccal mucosal scraping for HLA						X ⁸	X ⁸	X ⁸	X ⁸	X ⁸		
Pregnancy test	X ⁴				X ⁵		X ⁵		X ⁵	X ⁵		
Amount of blood to be drawn	1-2 tsp	4 – 6 tbs ⁶	4 – 6 tbs ^{3,6}		4 – 6 tbs ⁶	4 – 6 tbs ⁶	4 – 6 tbs ⁶	4 – 6 tbs ⁶	4 – 6 tbs ⁶	4 – 6 tbs ⁶		
Time required per visit	~3 hour	~9 hours	~3 hours	~3 hours	~9 hours	~1 hours	~1 hours	~1 hours	~9 hours	~9 hours	~3 hours	~3 hours

¹ will be obtained after 24 week build-up

² will check only peanut -specific IgE at the screening visit.

³ will be obtained at week 6, 12, 18, 24, 30, 36, 42, 48 of build-up phase only.

⁴Beta HCG serum pregnancy test

⁵ Urine pregnancy test

⁶Maximum amount of blood drawn (4 mL/kg)

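### Read literally, the steroid note in 3.2 and the pregnancy rules in 6.5 to 6.7 end the safety follow-up that 6.12 provides, and no visible step obtains a pregnancy outcome

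*Combined protocol and SAP*

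**What the plan says.** All references are to the combined protocol and SAP.

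- **Section 3.2, note.** "Subjects will be taken off the study if treatment with any dose of steroid is required for greater than 21 days". The same sentence adds a second trigger: "if oral systemic corticosteroids are required greater than twice per year for asthma exacerbations".
- **Section 6.5.** "If the subject is pregnant she will be dismissed from the study". Sections 6.6 and 6.7 repeat this and also cancel the food challenge.
- **Section 6.11.** The opening rule is "No subject initiating therapy in this trial will be replaced". Seven individual stopping rules follow, then three reasons for ending participation: consent withdrawal, loss to follow-up and death. The rules nearest to the steroid triggers are "Any participant is diagnosed with moderate to severe asthma based on the NHLBI guidelines" and "Any participant needs treatment with greater than medium daily doses of inhaled corticosteroids".
- **Section 6.12.** "Participants who prematurely discontinue treatment with study drug will remain in the study until normal termination". Willing subjects are followed for the whole study, give blood for the mechanistic work, and are to "be monitored for accidental ingestions and safety parameters".
- **Section 7** acknowledges possible significant risk to an unborn child. **Section 12.2** makes a congenital anomaly or birth defect a serious adverse event.
- **Section 12.5** follows events still open at the end of the study for 30 days after the last dose, and follows serious or treatment-related ones until they resolve.

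**The concern.** Section 6.12 separates stopping treatment from leaving the study, which is what a trial with a safety primary outcome needs. The note in 3.2 and the pregnancy rules do not make that separation. A coordinator who follows them as written would close the child's participation, and new adverse events after that date would not be collected.

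This matters because the exits may be related to the outcome. Lower-respiratory symptoms are graded as allergic reactions in Table 8, so a child who needs prolonged or repeated systemic steroids for wheeze may be one who is reacting to the peanut dose. For pregnancy, the protocol recognises a risk to the fetus, but the visible text provides no way of learning whether harm occurred.

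**Working it through.** The plan states no figure on this point, so the check is mainly a comparison of text.

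**Step 1: which rule governs a child who meets the steroid trigger?** Under 3.2 the child leaves the study. Section 6.12 covers participants who stop study drug early, with no restriction to the causes in 6.11, so on its own terms the child stays. No sentence says which prevails.

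**Step 2: does 6.11 settle it?** Neither systemic steroid duration or frequency nor pregnancy is among the seven stopping rules or the three termination reasons. The steroid limit appears only in a note to the exclusion criteria. The opening of section 6 allows oral corticosteroids during the rest of the study if needed, with no limit and no reference to 3.2. Staff working from 6 and 6.11 could therefore miss the rule.

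**Step 3: where do the pregnancy exits fall?** The schedule and sections 6.5 to 6.7 place urine tests at maintenance months 0, 12, 24 and 25. At month 25 the participant has already avoided peanut for four weeks, so there is no study treatment left to discontinue. Follow-up until the normal end of the study also adds little for a pregnancy found at month 24 or 25. Obtaining the outcome therefore needs its own instruction.

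**Step 4: does the adverse event section reach the birth?** Section 12.2 lists birth defect as a seriousness criterion. Pregnancy itself is not named as an adverse event or a serious adverse event. The rule in 12.5 of following to resolution applies to events already open, and an uncomplicated pregnancy is not clearly one. The only fixed period in 12.5 is 30 days from the last dose. No visible passage says that the outcome is obtained.

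**Step 5: scale.** Inputs: target of 15 children (sections 1 and 10.1); no replacement (6.11).

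- One child as a share of the cohort: 1/15 = 6.7%.
- With zero events among n children, the one-sided 95% exact upper bound on an event rate is 1 − 0.05^(1/n). For n = 15 this is 18.1%; for n = 14 it is 19.3%. Losing one child completely widens the bound by 19.3 − 18.1 = 1.2 percentage points. These exits lose only the time after exit, so the actual loss of precision is smaller.
- If the unobserved time held an event that would otherwise have been the child's first of its kind, the observed proportion would be understated by 1/15 = 6.7 percentage points.

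The documents give no frequency for either trigger, so an expected loss cannot be computed.

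**The case against.** The strongest reply is that the exit wording is loose language for stopping treatment. The protocol does this elsewhere. Item C of the dose-adjustment algorithm in Appendix II says that a Grade 4 reaction ends the study for that patient and then offers a peanut equivalent, while 6.11 lists the same event as a stopping rule. Section 7 makes failure to carry epinephrine a ground for termination from the study, and 6.11 again treats it as a stopping rule. Since 6.12 is general, a steroid-related stop could already be handled there. This is a fair reading, and it lowers the severity. It does not remove the literal conflict, and it supplies no pregnancy-outcome step.

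Other limits also stand. The triggering event is recorded under 12.5. Section 6.12 covers willing subjects only. Birth control is an entry condition. The consent pages were not available for review, and the visible section numbering passes from 4 to 6, so pregnancy wording elsewhere cannot be excluded.

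A reader might infer more than the documents support:

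- **That the 3.2 note catches inhaled steroids.** Its preceding sentences name prednisone, methylprednisolone and prednisolone and set the same 21-day limit. In context it concerns those systemic agents.
- **That the same asthma problem is given two follow-up rules.** Whether frequent oral courses would also meet the moderate-to-severe asthma criterion in 6.11 depends on NHLBI definitions that the protocol cites but does not reproduce.
- **That the eosinophilic esophagitis stopping rule is compromised.** This needs a steroid exit, loss of contact, a later diagnosis, and that case being decisive. The documents give no frequency for any of these.

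**Conclusion.** The point holds as a minor inconsistency in safety follow-up. Read literally, 3.2 and 6.5 to 6.7 contradict 6.12; neither trigger is in 6.11; and the visible text has no step to obtain the outcome of an exposed pregnancy.

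Its size is one child in 15 (6.7%) per exit, with both triggers probably uncommon. The conclusion assumes that the exit wording would be applied as written and that the unseen consent pages do not already provide for contact. If the wording was only loose, the edit simply states the intent.

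It would be wrong to infer that the main results are at risk. The 9.2.1 comparison of tolerated dose is little affected. The gap concerns events after exit, and pregnancy outcome in particular. Label: cheap improvement.

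**What to change.** 1. **Section 3.2.** Reword the sentence as: *Subjects will be discontinued from study treatment, and followed under 6.12 if willing, when systemic corticosteroids are needed for more than 21 days or oral systemic corticosteroids are needed more than twice in a year for asthma exacerbations.* Add the same systemic-steroid wording, and *pregnancy*, to the individual stopping rules in 6.11, so that the two sections match.
2. **Sections 6.5, 6.6 and 6.7.** Replace the dismissal wording with: *receives no further study dosing or food challenges and is followed under 6.12 if willing.* This also works at month 25, when dosing has already stopped.
3. **Section 6.12.** Add: *If a participant becomes pregnant, dosing, food challenges and research blood draws stop; safety follow-up continues if she is willing, and the pregnancy outcome is obtained by contact with the family, even if this falls after the end of the study.*

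The cost is wording in four places, two bullets in 6.11 and one sentence in 6.12, plus a little follow-up contact and possibly a consent or assent edit. Sample size and analysis do not change. A child who stops for steroids is offered only the follow-up and blood draws that 6.12 already offers; a pregnant participant has no research blood draws.

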4. RECRUITMENT METHODS AND CONSENTING PROCESS

Subjects meeting criteria for participation in the study will be recruited from [name] clinic at Texas Children's Hospital, Allergy and Immunology Section. They will be informed of the consent procedure and study details as outlined in this document.

Subjects that are not patients of [name] will be recruited by referral from other Allergy and Immunology physicians within Texas Children's Hospital and by referral from community

physicians. Physicians in the community will learn about the study by word of mouth or by talking with [name] and will ask their patients to contact [name] or their staff directly. Printed materials will not be used to recruit subjects and subjects not seen by [name] will not be contacted by [name] or their staff directly for recruitment purposes. Details of the study including inclusion criteria and exclusion criteria will be discussed with prospective subjects when they contact [name] or their staff. We will target underrepresented patients for enrollment to reflect the patient pool diversity.

Consent will be required from a parent or legal guardian of all study subjects and will be documented in the research records. Subjects will be consented in a private location by study personnel. Measures will be taken to minimize undue influence or coercion. Assent will be required of all minor subjects 7 years of age and over.

This protocol is be registered on [ClinicalTrials.gov](https://clinicaltrials.gov).

6. TREATMENT/INTERVENTION PLAN

The study will require approximately 36 visits over approximately 40 months. Subjects will come to Texas Children's Hospital in Houston, TX for all desensitization procedures. Subjects will discontinue antihistamines (for example, Benadryl or Claritin) for 7 days before the first visit for the entry food challenge and the initial dose escalation. Dose escalation means to give a larger amount of study protein than the subject was previously taking. Each time the dose is increased the subject will need to come to Texas Children's Hospital in Houston, TX to be observed. Subjects may take antihistamines during the study but must stop them one week prior to the first visit for the entry food challenge. Once 3900 mg of peanut protein or highest tolerated dose is achieved, the subject will switch to a peanut equivalent dose for the maintenance phase.

Subjects must be off oral corticosteroids (for example, Prednisone) within one month of the procedure but they may be taken during the remainder of the study if needed. For the subjects safety prior to any food challenge an IV catheter needle will be inserted into a vein in the subject's arm in case medications are needed for treatment of a reaction. EMLA® cream or L-M-X®, a medicine put on the skin to numb it, may be applied to the skin prior to IV placement to make it less painful.

The subject will have blood drawn throughout the study. Approximately 1-2 teaspoons will be drawn at the screening visit and 4 to 6 tablespoons will be drawn approximately every 6 weeks during the first year and every 6 months during the second and third years. The total amount of blood for the entire study will be from 60-90 tablespoons.

6.1. Screening Procedures:

This visit should take approximately 3 hours.

The following information will be collected:

- Consent and assent;
- Physical exam and medical and diet history;
- Vital signs (pulse, respiratory rate, blood pressure, weight, height, temperature);
- Blood tests (1 teaspoon to measure peanut-specific IgE);
- Allergy skin prick tests (A small amount of allergen dissolved in solution is placed on the skin, and the skin is scratched allowing the solution to enter the skin. The presence of a wheal indicates sensitivity to the allergen. The subject will experience itching at the site of the procedure if they are sensitized to peanut. The starting concentration will be the standard peanut extract 1:20 wt/vol with serial dilutions of 1:200, 1:2000, 1:20,000, and 1:200,000 wt/vol as well as oat, wheat, positive (histamine) and negative (saline) controls.)
- Demographic information (age, sex, ethnic origin).
- Serum pregnancy test for menstruating females (1/10 tsp of blood)

- Spirometry: Spirometry will be attempted in all participants. If valid spirometry results are not successfully obtained, the attempt is documented and peak flow measures will be accepted for the entry criteria with results >90% of predicted. For participants that are able to complete spirometry, FEV1 must be greater than 90% predicted.
- Peak flow will be determined for the patient.
- Screening visit will occur within 1 month of the DBPCFC.

6.2. *Study Medication/Intervention:*

The product to be used in this study is only peanut flour. Subjects that cannot tolerate the initial low doses of peanut flour will not be enrolled. The peanut flour will be given in small pre-measured soufflé cups containing the amount of peanut flour that needs to be eaten for one dose.

The flour will be received from the University of North Carolina at Chapel Hill Manufacturing Facility (See Letter of Authorization). Lot-to-lot testing will be performed by the manufacturer on each batch of new peanut flour to ensure accuracy of dosing potency. The process involves running an SDS-PAGE gel with the previous lot and the new lot. Densitometric scanning is then performed to compare Ara h 1 levels and Ara h 2 levels. The University of North Carolina at Chapel Hill Manufacturing Facility has defined the acceptable ranges to be less than 30% for Ara h 1 and 20% for Ara h 2. If a lot fails the test, the batch is discarded and a new lot of peanut flour is ordered. The peanut protein will be received by the Center for Cell and Gene Therapy at Baylor College of Medicine (CAGT).

The CAGT is a Good Manufacturing Practice (GMP) compliant facility (See Letter of Authorization) and is accredited by the Foundation for the Accreditation of Cellular Therapy (FACT), the College of American Pathologists (CAP) and is CLIA registered. The protein doses will be monitored and dispensed by the CAGT GMP Facility.

The drug would be stored in the cold room (2-8°C) within the clean room area restricted to CAGT GMP Facility Staff. It is on continuous temperature monitoring via our Isensix system. In the case of an alarm staff is informed via pager system. Alarms and monitoring data are also full backed up by Isensix in San Diego. This drug will be stored in a dedicated facility away from other allergens and will be handled in a separate room on a separate air handling systems.

The pre-measured soufflé cups will be transported by a clinical research staff member within Texas Children's Hospital controlled environment.

The peanut flour will be used within the manufacturer's expiry date and our center will follow all instructions provided by the manufacturer.

One dose of peanut flour is taken per day. Prior to taking the dose the subject must eat a snack high in carbohydrate and fat such as a bagel or chips and then eat the peanut flour mixed into liquid or another food such as apple sauce or ice cream.

The vehicle food for each subject will be a food, to which the subject is not allergic. The subject will need to eat the peanut flour at approximately the same time every day. After eating the peanut flour the subject will need to be with a supervising adult for the next 2 hours so they can monitor for any possible reaction. The subject cannot go to school within 2 hours of eating the

peanut flour and cannot go to bed within 2 hours of eating the peanut flour. After 1 month, if there are no adverse events with the maintenance dose or highest dose tolerated, the provider will have the option of decreasing the observation period to 1 hour with no physical activity to occur for 1 hour.

Subjects who miss one to two days of the daily dose will continue at their present dose. Those who miss 3 to 4 days of the daily dose of study product will receive their next dose at the Allergy and Immunology Clinic and be observed for a minimum of 2 hours after dosing to assure safety with dosing. Those who miss more than 4 days will return to the Allergy and Immunology Clinic for a graded challenge. The subject will switch to a peanut equivalent dose once he/she reaches the maintenance dose or highest dose achieved.

The dosing guidelines for peanut flour will continue to be followed.

Table 1. Schedule during build-up phase for missed daily doses (time intervals from missed doses)
• Up to 2 days, continue doses as scheduled.
• 3-4 consecutive days after missed dose; repeat previous doses but dose will be given in the Allergy/Immunology Clinic.
• More than 4 days after missed dose, patient will return to Allergy/Immunology Clinic for a graded challenge.

6.3. Entry Oral Food Challenge (approximately 9 hours):

- Amount of blood to be drawn at this visit: Blood drawn to check the peanut-specific IgE, IgG and IgG4 levels, and cellular immune studies and basophil activation studies will be drawn and evaluated at Texas Children’s Center for Human Immunobiology (Baylor College of Medicine) for analysis.

IgG and IgG4 are antibodies that may have a role in tolerating peanut. They will be followed throughout the study and we will evaluate how they are changing while the subject is on therapy. In addition we will be obtaining blood for the immune cell studies.

- In order to obtain sufficient quantity of cells we will collect the maximum amount of blood allowable as defined by Texas Children’s Hospital based on the subject’s weight. This will range from 4 to 6 tablespoons total of blood drawn for the visit.
- Spirometry: Spirometry results or peak flow measures will be accepted. For participants that complete peak flow the results must be > 90% of predicted. For participants that complete spirometry, FEV1 must be greater than 90% predicted on the day of the challenge to participate in the food challenge.
- Targeted History and Physical Exam and Diet History: A brief medical and diet history will be obtained and a focused physical exam will be performed.

- DBPCFC: Subjects eligible for the study (peanut-specific immunoglobulin E level greater than 7kU/L AND a positive skin prick test to peanut) will come to Texas Children's Hospital in Houston for a Double Blind Placebo Controlled Food Challenge (DBPCFC) to the study protein to determine if the subject is allergic to peanut. The table below labeled Table 2 details dosing for the initial DBPCFC and also shows the dose at which the subject will start treatment correlating with the dose at which a reaction is noticed.

Table 2. Entry Double-Blinded Placebo Controlled Food Challenge Protocol and Starting Dose of Oral Immunotherapy to be Initiated				
Dose Number	Approximate Dose Weight (PEANUT FLOUR)	Approximate Dose Weight (PEANUT PROTEIN)	Cumulative Dose Weight (peanut protein)	Starting Dose of OIT if Subject Reacts
1	1 mg	0.5 mg	0.5 mg	Ineligible
2	2 mg	1 mg	1.5 mg	Ineligible
3	10 mg	5 mg	6.5 mg	1.8mg
4	30 mg	15 mg	21.5 mg	3.6 mg
5	108 mg	54 mg	75.5 mg	14.4 mg
6	150 mg	75 mg	150.5 mg	28.8 mg
7	200 mg	100 mg	250.5 mg	40 mg
8	500 mg	250 mg	500.5 mg	120 mg
9	1000 mg	500 mg	1000.5 mg	300 mg
10	2000 mg	1000 mg	2000.5 mg	750 mg

The DBPCFC visit will last approximately 9 hours. The food challenge may be performed in one day or split into two days. The subject will discontinue antihistamines (for example Zyrtec or Claritin) for 7 days before the procedure and must be off oral corticosteroids for one month before the food challenge.

A DBPCFC consists of eating both a food to which the subject may be allergic (peanut) and eating a placebo at different times. A placebo is a substance that is similar to the test substance in appearance, smell, and taste. The peanut protein is a flour and will be given mixed with either juice (at lower doses) or with a food like baby food. The placebo is oat flour for peanut DBPCFC and will be given in the same manner.

The food will be given in a “double-blinded” fashion under observation at Texas Children's Hospital in Houston. During both of the feedings, the food protein to be given during the challenge will start with the equivalent of less than 1/100th of a peanut and progressively larger doses will be given at 15 minute intervals if the subject does not have an allergic reaction to one of the doses. If the subject does have a reaction to one of the doses, the dosing of study protein will be stopped and the allergic reaction will be treated with an antihistamine and/or epinephrine or other emergency medications which may include but is not limited to bronchodilators, oral or injectable steroids, or H2 blockers). Overall, patients with a history of a prior clinical reaction to peanut will be observed for 120 min after ingestion of the last tolerated dose of peanut protein during the DBPCFC. Patients who have not had previous oral exposure to peanut may

demonstrate a delayed immune response, given the lack of prior peanut exposure. Therefore, those subjects will be observed for a longer duration of 150 minutes. (21-24) The highest dose of peanut protein will be equivalent to 4 peanuts. The initial dose of therapy will be determined by the provider and will be slightly lower than the amount at which the subject reacted to during the DBPCFC (Table 2).

6.4. Buildup Visit Weeks 0 – 50 or until highest tolerated dose (maintenance dose) is reached (approximately 3 hours per visit):

- First build-up visit will occur within 1 month of the DBPCFC. If the subject has symptoms with the first home dose in the clinic, the child may return for a lower dose visit up to two times. If he/she cannot tolerate the 1.8mg dose, the subject will be excluded from the trial.
- Amount of blood to be drawn: Every 6 weeks at weeks 6, 12, 18, 24, 30, 36, 42, 48, etc. we will draw up to 4-6 tablespoons of blood (based on the subject's weight) for immune studies, peanut-specific IgE, IgG, and IgG4 and basophil histamine release assays. Blood will not be drawn at the other build-up visits.
- Peak Flow: Peak flow measures will be accepted with results >90% of predicted.
- Allergy Skin Prick Tests: At week 24, endpoint dilution skin testing to peanut will be repeated. The procedure will be performed as described under section 6.1 "Screening Procedures."
- Targeted History and Physical Exam and Diet History: A brief medical and diet history will be obtained and a focused physical exam will be performed.
- Review Home Symptom Diary: At each visit we will review any symptoms experienced while taking the food protein.
- Epinephrine injector will be checked for expiration date and parents/guardian will demonstrate proper use.
- Dose Escalation: The subject must return in no less than 10 days after each visit to receive an increased amount of peanut protein. (See Table 3.) At each visit the subject will be given a slightly larger amount of peanut protein than he or she was receiving prior to that visit. After the first visit the subject will be taking at least the equivalent of approximately 1/100th of a peanut daily and once the subject gets to the maintenance dose he or she will be taking the equivalent of approximately 15 peanuts daily. The length of time the participant is in the build-up phase is dependent on the starting dose determined from DBPCFC and how well each subsequent buildup dose is tolerated. The subject will build up to 3.9 grams of peanut protein or the highest dose tolerated. This is known as the maintenance dose.

Table 3. Dose Escalation Table

Weeks On OIT	Dose No.	Protein Per Soufflé portion cup (mg)	PN flour weight per soufflé portion cup (mg)
0,1	1	1.8	3.6
2,3	2	3.6	7.2
4,5	3	7.2	14.4
6,7	4	14.4	28.8
8,9	5	28.8	57.6
10,11	6	40	80
12,13	7	60	120
14,15	8	80	160
16,17	9	100	200
18,19	10	120	240
20,21	11	240	480
22,23	12	300	600
24,25	13	450	900
26,27	14	600	1200
28,29	15	750	1500
30,31	16	900	1800
32,33	17	1050	2100
34,35	18	1200	2400
36,37	19	1350	2700
38,39	20	1500	3000
40,41	21	1800	3600
42,43	22	2100	4200
44,45	23	2400	4800
46,47	24	3000	6000
48,49	25	3600	7200
50,51	26	3900	7800

6.5. Follow-up Visits (every 6 months for 24 months after maintenance dose is reached) (approximately 3 hour per visit):

Once the maintenance dose is achieved, the patient will follow up in the clinic 2 weeks later to ensure the higher dose is being tolerated and will switch to a peanut equivalent

dose (Table 4). The first dose of the peanut equivalent will be given in the hospital setting. The family will be instructed on how to administer peanut equivalent dose. The subject will continue to follow the “Instructions for Daily Home Doses” as used for peanut flour dosing. This will be considered “Month 0”. The participant will remain on this dose for 24 months and follow-up visits will occur every 6 months. The subject will continue to follow the peanut flour dosing guidelines. A food challenge will be performed within 1 month of the “Month 0” visit.

Table 4. Peanut Equivalent Dose

Peanut Product	Peanut Protein (gram) /serving	Maintenance Dose (3900mg peanut protein)	Alternative Dose (if maintaining below 3900mg)
Creamy Peanut Butter *Peter Pan or Reese’s Creamy Peanut Butter*	8 grams=2 Tablespoons	1 Tablespoon	1300 mg =1 teaspoon 325mg=0.25 teaspoon
JIF Peanut Powder	8 grams=3 Tablespoons	1.5 Tablespoons	
PB2 Powdered Peanut Butter (Bell Plantation)	5 grams=2 Tablespoons	1.5 Tablespoons	1300 mg= 1.5 teaspoon 300 mg = 3/8ths of a teaspoon
Dry Roasted Peanuts	0.175 grams=1 peanut	22 peanuts	1300 mg = 7 and ½ peanuts 350 mg = 2 peanuts
Peanut M&M’s	0.15 grams=1 piece	26 pieces	1300 mg = 8 and 2/3 pieces 300 mg=2 pieces
Reese’s Pieces Candy	0.078 grams=1 piece	50 pieces	1300 mg = 16 and 2/3 pieces 312 mg = 4 pieces
Reese’s Peanut Butter Cups Miniatures	0.8 grams=1 miniature cup	~5 miniature cups	1300 mg = 1 and 5/8 th cups 300 mg = 3/8 th cup

Other approved alternative:			
-----------------------------	--	--	--

- If the subject experiences no adverse events with the maintenance dose or highest dose tolerated after 1 month, the provider will have the option of decreasing the observation period at home to 1 hour. The subject will need to avoid any form of physical activity 2 hours after ingestion.
- Peak Flow: Peak flow measures will be accepted with results >90% of predicted.
- Amount of blood to be drawn: After maximum tolerated dose is achieved at approximately 1 year (drawn at Visit 30- Month 0 DBPCFC) and every 6 months afterwards, we will draw up to 4-6 tablespoons of blood (based on the subject's weight) for peanut-specific IgE, IgG, and IgG4, cellular immune studies and basophil histamine release assays until the end of the protocol.
- Allergy Skin Prick Tests (PST): Endpoint dilution skin testing to peanut will be done at month 0 and month 12 visits.
- Targeted History and Physical Exam and Diet History: A brief medical and diet history will be obtained and a focused physical exam will be performed.
- Epinephrine injector will be checked for expiration date and parent/guardian will demonstrate proper use.
- Review Home Symptom Diary: At each visit we will review any symptoms experienced while taking the food protein.
- Administer Peanut Equivalent Dose: The first dose of the peanut equivalent will be given in the hospital setting followed by a 2 hour observation period.
- Urine Pregnancy Test: For females of reproductive potential a urine pregnancy test will be performed at month 0 and month 12 visits. If the subject is pregnant she will be dismissed from the study.

6.6. 0 Month Maintenance Study Food Challenge Visit (approximately 9 hours)

- The food challenge will need to be completed within 1 month of the "Month 0" visit.
- Amount of blood to be drawn: At this visit, we will draw up to 4-6 tablespoons of blood (based on the subject's weight) for peanut-specific IgE, IgG, and IgG4 and cellular immune studies, and basophil histamine release assays
- Spirometry or Peak Flow: Spirometry will be attempted in all participants. If valid spirometry results are not successfully obtained, the attempt is documented and peak flow measures will be accepted for the entry criteria with results >90% of predicted. For participants that are able to complete spirometry, FEV1 must be greater than 90% predicted on the day of the challenge to participate in the food challenge.

- Targeted History and Physical Exam and Diet History: A brief medical and diet history will be obtained and a focused physical exam will be performed.
- DBPCFC: The subject will come to Texas Children's Hospital in Houston for a Double Blind Placebo Controlled Food Challenge (DBPCFC) to the study protein (peanut) to determine if he or she is still allergic to peanut or can tolerate peanut.

The DBPCFC visit will last approximately 9 hours. The food challenge may be performed in one day or split into two days. The subject will discontinue antihistamines (for example Zyrtec or Claritin) for 7 days before the procedure and must be off oral corticosteroids for one month before the food challenge.

